### Recording and Notification of Adverse Events

At each contact with the participant, the study team members will seek information on AEs by specific questioning and, as appropriate, by examination. Information on all AEs

will be recorded immediately in the source document, and also in the appropriate AE module of the eCRF. All clearly related signs, symptoms, and abnormal diagnostic procedures results will be recorded in the source document.

Any event meeting the reporting guidelines per HRP 801 INVESTIGATOR GUIDANCE: Prompt Reporting Requirements, will be reported to the AdventHealth Orlando IRB.

## **Safety Monitoring Plan**

### **Safety Monitoring**

Adverse events will be documented and reported by the study coordinator, the Principal Investigator, and other TRI-MD staff. Research and safety data will be reviewed by the Principal Investigator. This review will take place at regular meetings with the research coordinator and study physician where the safety labs for each new participant will be reviewed. Other items discussed will include progress or AEs occurring in the following: subject confidentiality, subject recruitment, and the informed consent process. All AEs and unexpected and/or severe AEs will be reported to the AdventHealth Orlando IRB per HRP 801 INVESTIGATOR GUIDANCE: Prompt Reporting Requirements. The TRI-MD has a standing committee that meets monthly to review all AEs in the clinical trials and will additionally be charged with review of the study.

### **Data and Safety Monitoring Board (DSMB) or Equivalent**

Not applicable.

## **ETHICAL CONSIDERATIONS**

Participation in this study is voluntary. Participants may decide not to participate in this study or may withdraw from this study at any time without penalty or loss of benefits. No vulnerable populations will be studied in this protocol.

### **Sharing of Results with Subjects**

Participants will be offered the opportunity to meet with the Principal Investigator or designated medical staff to review the results of their laboratory assessments or other standard clinical data. Copies of their testing results will be made available to the participants upon request. In addition, the Principal Investigator or designated study staff will provide an overview of the study's outcome to the participant, when available, if he or she requests the information.

## **FUNDING SOURCE**

This study will be externally funded by Pfizer Inc.

## **PARTICIPANT STIPENDS OR PAYMENTS**

After the participant's completion of all study visits, a total amount for the study will be \$1,000-1,375.00. A Mastercard® payment will be processed with the Dollar amount per visits completed as indicated in the table below. Mastercard® payments may take up to 3 business days to be

processed, once requested. In the event the participant is unable to complete all study visits the payment will be prorated.

The payments are broken into two payments: Screening Visit 1 through Visit 5 (after completion of all visits through the 12-week time point), and Visits 6-7 (after completion of the remaining visits ending at the 52-week time point).

Compensation for Baseline Visit 1 and Visits 4-7 will vary, depending whether a stool sample is provided and the dual cholate test is completed.

Participants who agree to take part in this study will be paid for completed procedures according to the following schedule:

Visit	Total
Screening Visit 1	\$50.00
Screening Visit 2	\$125.00
If both screening visits are combined, the payment will also be combined	
Baseline Visit 1 Stool - \$25.00; Dual cholate \$50.00	\$50.00-125.00
Baseline Visit 2	\$125.00
Visit 3 (Surgery)	\$150.00
Visit 4 Stool - \$25.00; Dual cholate \$50.00	\$125.00-200.00
Visit 5 Stool - \$25.00; Dual cholate \$50.00	\$125.00-200.00
Visit 6 Stool - \$25.00; Dual cholate \$50.00	\$125.00-200.00
Visit 7 Stool - \$25.00; Dual cholate \$50.00	\$125.00-200.00
TOTAL	\$1,000-1,375.00

## PUBLICATION PLAN

TRI-MD faculty and staff will adhere to POLICY-TRI-ADM-005 (Access to Clinical Trial Data for Publication Purposes).

## APPENDIX A. SCHEDULE OF EVENTS

Description	Screening Visit 1	Screening Visit 2	Baseline Visit 1	Baseline Visit 2	Surgery	Post-Surgery			
Visit Number	SV1	SV2 l	BLV1 m	BLV2	V3	V4	V5	V6	V7
Day a	Varies	Varies	Varies	Varies	1	42 ±7	84 ±7	182 ±14	364 ±14
Physical Exam b	X	X							
Provider time to explain study	X								
Assess participant eligibility	X	X			X				
Informed consent c	X								
Demography c	X								
AE/ConMed review		X	X	X		X	X	X	X
Drug Alcohol Tobacco Screen/AUDIT questionnaire		X							
Height and body weight d	X	X	X	X	X	X	X	X	X
Body Mass Index (BMI)	X	X	X	X	X	X	X	X	X
Vital signs b	X	X	X	X	X	X	X	X	X
Screening Lab assessments (fasting) e		X							
Urine pregnancy test		X	X	X	X	X	X	X	X
Urinalysis		X							
Urine drug screen		X							
HIV, HBV, HCV screen		X							
Hepatic panel			X	X		X	X	X	X
Hemoglobin				X					
Pre-surgery diet f				X					
SoC Bariatric surgery					X				
Liver biopsy g					X				
Blood collections for: OWL Metabolomics Nordic Bioscience			X	X		X	X	X	X
Blood collections for: Biobanking h			X			X	X	X	X
Stool Collection i			X			X	X	X	X
HepQuant SHUNT Dual Cholate Liver Diagnostic Kit j			X			X	X	X	X
IMAGING									
FibroScan®		X		X		X	X	X	X
MRI k		X		X		X	X	X	X

Current Version Date:

24OCT2019

Previous Version Date:

05SEP 2019

Research Study protocol template version date 11/3/2016

IRBNet #: 1000376

Page 43 of 46

## SCHEDULE OF EVENTS, cont.

Abbreviations: AE = adverse event; AUDIT = Alcohol Use Disorders Identification Test; CH = Celebration Health; ConMed = concomitant medication; HBV = hepatitis B virus; HCV = hepatitis C virus; HIV = human immunodeficiency virus; MRE = magnetic resonance elastography; MRI = magnetic resonance imaging; SoC = standard of care; TRI-MD = Translational Research Institute for Metabolism and Diabetes.

**Note: Screening Visit 1 (SV1) may occur either at CH or TRI-MD. Surgery (V3) occurs at CH. All other visits and procedures, including the combination screening visit (if applicable), occur at TRI-MD.**

- a. Pre-surgery time points will vary based upon insurance requirements, length of diet, and other clinical needs.
- b. Performed by CH provider as a part of standard of care procedures at SV1 and at TRI-MD at indicated visits per our standard research procedures.
- c. Performed by CH study coordinator/CH provider.
- d. Height measured at SV1 and SV2 only; weight measured at designated visits for calculation of body mass index (BMI).
- e. Screening laboratory assessment are collected at SV2 or the combination SV1/SV2 visit and include: complete blood count (CBC), platelet count, comprehensive metabolic panel (CMP), lipid panel, prothrombin (may include prothrombin time [PT]/international normalized ratio [INR]/partial thromboplastin time [PTT]), activated partial thromboplastin time (APTT), , hemoglobin A1c (HbA1c), thyroid stimulating hormone (TSH) with reflex to thyroxine (T4), parathyroid hormone (PTH).
- f. The pre-surgery diet varies and occurs as per standard of care. BLV2 will occur during the last 5 days of the liquid diet.
- g. Liver biopsy for clinical histology and research. Participants without non-alcoholic steatohepatitis (NASH) upon biopsy will not continue longitudinal assessment. The Liver Biopsy is the final criteria determining the cohort (NASH vs NON-NASH)
- h. Blood collections for biobanking: plasma, serum, PAX DNA, P800 tube.
- i. Stool will be collected during clinic visit if possible. If not, a home stool collection kit will be sent home with participant.
- j. HepQuant SHUNT Dual Cholate Liver Diagnostic will be discontinued if there are any feasibility or tolerability issues.
- k. The TRI-MD liver fat percentage by Proton Density Fat Fraction (PDFF) will be used to ascertain eligibility. For participants that meet eligibility criteria at SV2, data will be sent to Perspectum and AMRA to generate PDFF and other liver endpoints from MRI data collected at SV2 and BLV2, V4, V5, V6 and V7.
- l. SV2 will occur as soon as possible after SV1.
- m. BLV1 will occur within a maximum of 28 days from SV2.

## APPENDIX B. ALCOHOL USE DISORDERS IDENTIFICATION TEST (AUDIT) QUESTIONNAIRE

Please circle the answer that is correct for you

1. How often do you have a drink containing alcohol?
 
Never Monthly or less 2–4 times a month 2–3 times a week 4 or more times a week
	
6. During the past year, how often have you needed a drink in the morning to get yourself going after a heavy drinking session?
 
Never Less than monthly Monthly Weekly Daily or almost daily

2. How many standard drinks containing alcohol do you have on a typical day when drinking?
 
1 or 2 3 or 4 5 or 6 7 to 9 10 or more
	
7. During the past year, how often have you had a feeling of guilt or remorse after drinking?
 
Never Less than monthly Monthly Weekly Daily or almost daily

3. How often do you have six or more drinks on one occasion?
 
Never Less than monthly Monthly Weekly Daily or almost daily
	
8. During the past year, have you been unable to remember what happened the night before because you had been drinking?
 
Never Less than monthly Monthly Weekly Daily or almost daily

4. During the past year, how often have you found that you were not able to stop drinking once you had started?
 
Never Less than monthly Monthly Weekly Daily or almost daily
	
9. Have you or someone else been injured as a result of your drinking?
 
No Yes, but not in the past year Yes, during the past year

5. During the past year, how often have you failed to do what was normally expected of you because of drinking?
 
Never Less than monthly Monthly Weekly Daily or almost daily
	
10. Has a relative or friend, doctor or other health worker been concerned about your drinking or suggested you cut down?
 
No Yes, but not in the past year Yes, during the past year

### Scoring the AUDIT

Scores for each question range from 0 to 4, with the first response for each question (e.g., never) scoring 0, the second (e.g., less than monthly) scoring 1, the third (e.g., monthly) scoring 2, the fourth (e.g., weekly) scoring 3, and the last response (e.g., daily or almost daily) scoring 4. For questions 9 and 10, which only have three responses, the scoring is 0, 2 and 4 (from left to right).

A score of 8 or more is associated with harmful or hazardous drinking, a score of 13 or more in women, and 15 or more in men, is likely to indicate alcohol dependence.

## APPENDIX C. Liver Disease Score Calculation

To further evaluate potential risk of NASH, we will calculate two different scores based on bloodwork and clinical data we are already collecting.

The AST to Platelet Ratio (APRI) score is calculated via the following formula:  
**(AST in IU/L) / (AST Upper Limit of Normal in IU/L) / (Platelets in 10^9/L)**

The Fibrosis-4 (FIB-4) Index for Liver Fibrosis is calculated with the following formula:  

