### **Inclusion Criteria**

To be eligible for this study, participants must meet the following inclusion criteria:

1. Age  $\geq 18$  years
2. Undergoing bariatric surgery (Roux-en-Y or gastric sleeve only) as part of clinical care.
3. Negative  $\beta$ hCG- level (female participants who become pregnant during the study will be withdrawn)
4. MRI:
  - for initial assignment to NASH cohort –
    - MRI-PDFF  $\geq 8\%$  (data generated by TRI-MD), and
    - magnetic resonance elastography (MRE)  $\geq 3.00$  kPa ([Chen 2011](#), [Dulai 2016](#), [Loomba 2016](#), [Costa-Silva 2018](#)); or
    - MRE  $\geq 2.70$  kPa ([Chen 2011](#)) with at least one of the following risk factors for NASH:
      - type 2 diabetes
      - metabolic syndrome
      - ALT  $\geq 1.5$  times the upper limit of normal
      - Fibrosis-4 score suggestive of NASH (advanced fibrosis): Age  $\leq 35$ : score not applicable; Age  $\geq 36$ :  $> 2.67$  ([McPherson 2017](#))
      - AST to platelet ratio of  $\geq 0.7$ , which is suggestive of NASH (significant fibrosis) ([Lin 2011](#))
  - for initial assignment to NAFLD or normal participants cohort –
    - No requirement for minimum MRI-PDFF, and
    - MRE  $\leq 2.50$  kPa ([Chen 2011](#), [Dulai 2016](#), [Loomba 2016](#), [Costa-Silva 2018](#))

Final Cohort assignment to be confirmed based upon results of liver biopsy  
(See [Figure 1](#))

5. Histopathology assessment of liver biopsy that confirms NASH diagnosis

6. Hemoglobin A1c (HbA1c)  $\leq 9.5\%$
7. Fasting triglycerides  $\leq 400$  mg/dL (4.5 mmol/L)
8. Body mass index (BMI)  $\geq 35\text{kg}/\text{m}^2$  ( $- 0.5 \text{ kg}/\text{m}^2$ ) when qualified for bariatric surgery
9. Able to speak and understand written and spoken English
10. Understands the procedures and agrees to participate by giving written informed consent
11. Willing and able to comply with scheduled visits, laboratory tests, and other study procedures

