The eligible population for enrollment in the full longitudinal study is subjects with biopsy-confirmed NASH. Liver biopsies will be collected at the time of the bariatric surgery procedure; however, in advance of the surgery, screening criteria based on liver imaging assessments will be applied in a sequential manner in effort to help identify eligible subjects.

The MR assessment performed at Screening Visit 2 will serve as the non-invasive qualification of subjects with NASH, which will be defined as those having a liver fat-fraction  $\geq 8\%$  and liver stiffness  $\geq 3.00$  kPa or MRE  $\geq 2.70$  kPa (Chen 2011) with at least one of the following risk factors for NASH: type 2 diabetes, metabolic syndrome, Screening labs or labs drawn within 30 days prior to SV2 (ALT  $\geq 1.5$  times the upper limit of normal, AST to platelet ratio of  $\geq 0.7$ , and/or Fibrosis-4 score suggestive of NASH: Age  $\leq 35$ : score not applicable; Age  $\geq 36$ :  $> 2.67$  (Lin 2011, McPherson 2017). See [Appendix C](#) for description of how the scores are calculated.

The TRI-MD PDFF calculation will be used for determination of eligibility. Only enrolled participants will have their MRI data sent to AMRA and Perspectum for PDFF analysis during the study timepoints indicated in [Appendix A: Schedule of Events](#). During the bariatric surgery procedure, subject inclusion will be confirmed following histological analysis of the liver biopsy. Following bariatric surgery, qualifying subjects will undergo periodic assessments out to 52 weeks post-surgery. In addition, subjects who either (1) do not meet the screening criteria for presumed NASH prior to surgery, or (2) meet the initial screening criteria, but do not meet the biopsy criteria for NASH diagnosis, will be considered for inclusion in a non-NASH cohort whose baseline assessments and perioperative biopsies will serve as control data, but for which no post-surgical longitudinal assessments will be performed.

A summary of the screening criteria for subject eligibility is provided in the decision tree diagram provided in [Figure 1](#).

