## Screening Laboratory Assessments

The following laboratory assessments are utilized to assess eligibility during the screening process:

- complete blood count (CBC)
- platelet count
- comprehensive metabolic panel (CMP)
- lipid panel
- prothrombin (may be prothrombin time [PT]/international normalized ratio [INR]/partial thromboplastin time [PTT])
- activated partial thromboplastin time (APTT)
- HbA1c
- thyroid stimulating hormone (TSH) with reflex to thyroxine (T4)
- parathyroid hormone (PTH)
- urine pregnancy test
- urine drug test
- HIV antibody
- HBsAg (Hepatitis B antigen) screen
- HCVAb (Hepatitis C antibody)

These are used concomitantly to assess general patient health and determine study eligibility ([Inclusion/Exclusion Criteria](#)).

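### As printed, the AST to platelet ratio in Appendix C cannot in practice reach the 0.7 eligibility cut-off; formula and cut-off need one scale

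*Combined protocol and SAP*

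**What the plan says.** Three places in the combined protocol and SAP bear on this score.

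- **Inclusion Criteria, item 4 (MRI).** A candidate may be assigned to the presumed-NASH cohort with MRE ≥2.70 kPa if at least one of five risk factors is present: type 2 diabetes, metabolic syndrome, raised ALT, a high Fibrosis-4 score, or an AST to platelet ratio of at least 0.7. The criterion glosses that last level with the words "which is suggestive of NASH (significant fibrosis") and cites a source for it.
- **Eligibility narrative at the end of Exclusion Criteria, before Figure 1.** This repeats the 0.7 cut-off and refers to Appendix C for a "description of how the scores are calculated".
- **Appendix C.** "The AST to Platelet Ratio (APRI) score is calculated via the following formula", it says, and then prints "AST in IU/L) / (AST Upper Limit of Normal in IU/L) / (Platelets in" 10^9/L). The line has no multiplier. No other section gives a scale factor, a different platelet unit or a different cut-off.

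On final cohort assignment, footnote g of the Schedule of Events (Appendix A) adds: "The Liver Biopsy is the final criteria determining the cohort".

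**The concern.** The cut-off and its only stated formula do not appear to share a scale. AST divided by its ULN is a number of order one in most people. Dividing it by a platelet count in the hundreds gives a few thousandths to a few hundredths, far below 0.7. Staff who followed Appendix C literally would never credit this risk factor.

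At stake is the screening classification of candidates for whom this score is the only possible qualifying risk factor. They would fail the presumed-NASH screen even where the ratio was meant to let them through. Their next step is then unclear. Inclusion criterion 4 requires MRE ≤2.50 kPa for the NAFLD or normal cohort, while the narrative before Figure 1 says only that people who miss the NASH screen will be considered for the non-NASH cohort.

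**Working it through.** **Inputs from the documents.** Cut-off 0.7 (Inclusion Criteria, item 4; narrative before Figure 1). Formula, read left to right: score = (AST / ULN) / P, with P the platelet count in 10^9/L (Appendix C). The documents contain no worked score to reproduce.

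**Assumptions.** The documents give no platelet range, AST range or ULN. I use P = 150, 250 and 400, AST from 1 to 10 × ULN, and ULN = 40 IU/L.

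**Step 1: AST needed to reach 0.7.** AST / ULN = 0.7 × P.
- P = 150: 0.7 × 150 = 105 × ULN (× 40 = 4,200 IU/L)
- P = 250: 0.7 × 250 = 175 × ULN (× 40 = 7,000 IU/L)
- P = 400: 0.7 × 400 = 280 × ULN (× 40 = 11,200 IU/L)

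**Step 2: platelets needed to reach 0.7.** P = (AST / ULN) / 0.7. This needs neither the assumed platelet range nor the ULN.
- AST 1 × ULN: 1 / 0.7 = 1.4 or lower
- AST 1.5 × ULN (the multiple used for the ALT risk factor in the same list): 1.5 / 0.7 = 2.1 or lower
- AST 3 × ULN: 3 / 0.7 = 4.3 or lower
- AST 10 × ULN: 10 / 0.7 = 14.3 or lower

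**Step 3: scores over the assumed range.**
- AST 1 × ULN, P = 400: 1 / 400 = 0.0025, or 0.4% of 0.7
- AST 3 × ULN, P = 150: 3 / 150 = 0.020, or 2.9% of 0.7
- AST 10 × ULN, P = 150: 10 / 150 = 0.067, or 9.5% of 0.7

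Even AST 20 × ULN with P = 50 gives only 20 / 50 = 0.40.

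**Step 4: could another grouping rescue the line?** Reading it as AST / (ULN / P) gives (AST / ULN) × P. At AST equal to ULN and P = 250 that is 250, so essentially everyone would pass. Neither grouping makes 0.7 a working threshold.

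**Step 5: who is affected.** The criterion lists PDFF ≥8% and MRE ≥3.00 kPa, or MRE ≥2.70 kPa with a risk factor. It can be read in two ways.
- *PDFF ≥8% applies to both MRE routes.* Affected: PDFF ≥8%, MRE 2.70 to <3.00 kPa and none of the other four risk factors. At MRE ≥3.00 kPa no risk factor is needed.
- *The second route stands alone.* Also affected: PDFF <8%, MRE ≥2.70 kPa and none of the other four. These candidates cannot use the first route, so they depend on a risk factor at any MRE from 2.70 kPa upwards.

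**The case against.** Nobody need dispute the arithmetic; the case against concerns cause and effect.

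First, a multiplier may have been lost when the PDF was read, and formula lines are where that is most likely. The extracted line has matched brackets and an intact exponent and reads as complete, but the text alone cannot settle it. The point therefore holds only for the formula as printed, and the source page should be checked.

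Second, the site may never have used the printed line. Appendix C names the score APRI and the cut-off cites a source, so staff may have computed the index from that source or with software. The documents do not say. A reader might infer that eligible candidates were wrongly screened out; nothing in the documents shows that this happened.

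Third, a reader might take the general sentence under Screening Laboratory Assessments, that the results help determine eligibility, as proof that Appendix C is an operative rule. It mentions neither the ratio nor Appendix C. The operative status comes from inclusion criterion 4 and from the narrative that points to Appendix C.

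Fourth, the consequence is small. Any one of five risk factors suffices, and failing the NASH screen need not mean leaving the study. This stands, and it keeps the point minor. It does not remove the mismatch.

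**Conclusion.** The point holds in conditional form. As printed, the Appendix C score cannot in practice reach 0.7: over AST of 1 to 10 × ULN and platelets of 150 to 400 × 10^9/L it runs from 0.4% to 9.5% of the cut-off. Those ranges are assumptions, but the conclusion does not hang on them, because AST at 3 × ULN would need platelets of 4.3 × 10^9/L or lower whatever range is assumed.

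The effect is confined to candidates whose presumed-NASH status turns on this score alone. A reader might infer that only the PDFF ≥8%, MRE 2.70 to <3.00 kPa band is exposed. The wording does not support so firm a limit, because it also allows a reading in which PDFF <8% candidates are exposed. On either reading the number cannot be determined from the documents and may be zero.

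Nor do the documents support a wider claim about the study's results. Biopsy decides the final cohort, and neither the power statements in Sample Size Determination nor the primary analysis uses this ratio. The documents also do not show whether the formula or the cut-off is the one in error. Severity: minor.

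**What to change.** Reconcile inclusion criterion 4, the narrative before Figure 1 and Appendix C so that formula and cut-off are on one scale, and confirm that scale against the source cited for the cut-off. Look at the original Appendix C page first: if a multiplier is printed there, nothing needs to change.

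Only if Appendix C was applied as printed, re-check in the screening records every candidate whose status turned on this score, under whichever reading of the PDFF and MRE conditions the site used.

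The cost is a one-line correction, plus that desk check if it is needed. No new data are required.

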**(Age x AST) / (Platelets x ∛(ALT))**

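### Appendix C, as extracted, prints FIB-4 with a cube root of ALT; if the source confirms it, the score runs high against the >2.67 cut-off on one narrow route to presumed NASH

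*Combined protocol and SAP*

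**What the plan says.** Inclusion criterion 4 gives two MRE routes to the presumed-NASH cohort. At 3.00 kPa or more no risk factor is needed. At 2.70 kPa or more the participant qualifies "with at least one of the following risk factors for NASH", and the list has five entries: type 2 diabetes, metabolic syndrome, ALT at least 1.5 times the upper limit of normal, FIB-4, and the AST-to-platelet ratio. The FIB-4 entry reads "Fibrosis-4 score suggestive of NASH (advanced fibrosis"; it does not apply at age 35 or under and requires a score above 2.67 from age 36.

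The text before Figure 1 repeats these criteria and sends the reader to Appendix C "for description of how the scores are calculated". Appendix C introduces its one version with "The Fibrosis-4 (FIB-4) Index for Liver Fibrosis is calculated with the following formula" and then prints "Age x AST) / (Platelets x ∛(ALT" (outer brackets trimmed). No units accompany this line, although the AST-to-platelet line above it has them.

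The initial assignment is provisional: "Final Cohort assignment to be confirmed based upon results of liver biopsy". Under Study Site(s)/Location(s) and Number of Subjects, participants without biopsy-confirmed NASH have no post-surgery study visits and may join the non-NASH group of 10.

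**The concern.** The formula is operative. The eligibility text points to it, nothing else in the documents defines the score, and any one listed risk factor is enough on the 2.70 kPa route. A cut-off carries meaning only with the formula it was set for. If 2.67 belongs to a square-root index and the site computes a cube-root one, the criterion becomes easier to meet, and it tracks age more closely than a label of advanced fibrosis suggests.

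At stake is screening accuracy. Some people would be counted as presumed NASH on unremarkable results, go through baseline assessments on that footing, and be more likely not to have NASH confirmed at biopsy, an outcome the protocol describes as unlikely.

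**Working it through.** **Inputs from the documents.** The printed formula (Appendix C); the cut-off above 2.67 at age 36 or over, and the MRE limits of 2.70 and 3.00 kPa (inclusion criterion 4). The documents give no worked FIB-4 value, so there is no stated figure to reproduce.

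**Assumptions.** The comparator is the square-root form. AST and ALT are in U/L and platelets in 10^9/L. The example values are illustrative, because the documents give no reference ranges.

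**Ratio of the two forms.**
- Printed: C = Age × AST / (Platelets × ALT^(1/3))
- Assumed: S = Age × AST / (Platelets × ALT^(1/2))
- C / S = ALT^(1/2 − 1/3) = ALT^(1/6), which depends on ALT alone.

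| ALT | C / S | 2.67 on the printed scale equals, on the square-root scale |
|---|---|---|
| 17 | 1.60 | 1.67 |
| 20 | 1.65 | 1.62 |
| 30 | 1.76 | 1.51 |
| 40 | 1.85 | 1.44 |

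The ratio keeps rising, to 2.08 at ALT 80. There, however, the separate ALT criterion may already apply: with an assumed upper limit of normal of 53, 1.5 × 53 = 79.5. The upper end of the range should not be used to size the problem.

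**Examples.** For age 55, AST 35, ALT 35, platelets 200:
- C = 55 × 35 / (200 × 3.271) = 1925 / 654.2 = 2.94
- S = 1925 / (200 × 5.916) = 1925 / 1183.2 = 1.63

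| Age / AST / ALT / platelets | Printed | Square root | Printed form above 2.67? |
|---|---|---|---|
| 55/35/35/200 | 2.94 | 1.63 | yes |
| 50/35/30/200 | 2.82 | 1.60 | yes |
| 36/40/40/150 | 2.81 | 1.52 | yes |
| 45/38/40/180 | 2.78 | 1.50 | yes |
| 60/35/35/250 | 2.57 | 1.42 | no |
| 55/35/35/250 | 2.35 | 1.30 | no |
| 50/30/30/250 | 1.93 | 1.10 | no |
| 40/25/25/250 | 1.37 | 0.80 | no |

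None of the eight crosses under the square-root form.

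**Age at which the cut-off is reached**, with AST = ALT = 30: age = 2.67 × platelets × root(30) / 30.

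| Platelets | Printed | Square root |
|---|---|---|
| 150 | 41.5 | 73.1 |
| 200 | 55.3 | 97.5 |
| 250 | 69.1 | 121.9 |

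Crossing on unremarkable values is therefore mainly a matter of age about 50 or over, or platelets about 200 or less.

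**Where it can act.** FIB-4 decides nothing at MRE 3.00 kPa or more, below 2.70 kPa, at age 35 or under, or when another listed risk factor is present. What remains is MRE 2.70 to below 3.00 kPa, age 36 or over, and FIB-4 as the only risk factor.

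**The case against.** The strongest objection is that the square root is nowhere in the documents. They contain one formula and one cut-off, and the printed formula gives scores on both sides of 2.67, so they show no internal contradiction. This stands as a limit: the inflation is conditional on the usual definition of an index that the protocol names but does not otherwise define.

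Second, everything turns on one small mark on a root sign in text read from a PDF by a program. This also stands, and it is why the source check comes first.

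Third, the reach is small. Participants are bariatric patients who qualified for surgery at a BMI of about 35 or more, and some will have another listed risk factor, such as type 2 diabetes or metabolic syndrome. The documents do not say how many are left.

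A reader might infer more than the text supports:
- **That unremarkable results generally cross.** They do not, as the table shows, and some crossings are marginal: 60/30/25 with platelets 230 gives 2.68, but with platelets 231 it gives 2.665.
- **That false positives contaminate the NASH results.** Biopsy sets the cohort, and participants without NASH have no post-surgery visits, so they cannot contribute a 12-week change in PDFF or MRE.
- **That they reach the control group improperly.** The section on number of subjects and the text before Figure 1 both provide for that move.
- **That biopsy would often fail to confirm NASH.** No figure in the documents supports a rate.

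**Conclusion.** The point holds conditionally. It rests on two things: that the source PDF really shows a cube root, and that the index and its 2.67 cut-off are meant on the square-root scale. If both are true, FIB-4 is overstated by about 1.6-fold at ALT 17 to 1.85-fold at ALT 40, and the rule acts like a cut-off of about 1.67 to 1.44. Some participants would then be initially assigned to presumed NASH on unremarkable results. The damage is confined to initial assignment within the MRE band and risk-factor pattern described above. The share affected is unknown, and the co-primary analysis in biopsy-confirmed NASH is not contaminated. If the sign is a reading artefact, there is no error in the root.

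**What to change.** 1. Check the root sign in the source version of Appendix C. If it is a square root, stop here.
2. If it is a cube root, reconcile the Appendix C formula with the named index and with the 2.67 cut-off in inclusion criterion 4 and the text before Figure 1. State the units (years, U/L, 10^9/L) and the source of the formula.
3. Record which formula the site actually used. Recompute FIB-4 for anyone initially assigned to presumed NASH on this criterion alone.

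The cost is a one-line correction and a short recalculation from laboratory values that Appendix C says are already being collected. If the square-root form is adopted, somewhat fewer people will qualify by this route. Cohort assignment by biopsy does not change.
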